4.6.1. Primary Efficacy Endpoint

4.6.1.1. Scale for the Assessment and Rating of Ataxia (SARA)

The severity of ataxia is assessed with the SARA, an 8-item clinical rating scale from 0 (no ataxia) to 40 (most severe ataxia). The total score is derived as the sum of the individual items, which include gait (0-8), stance (0-6), sitting (0-4), speech disturbance (0-6), finger chase (0-4), nose-finger test (0-4), fast alternating hand movements (0-4), and heel-shin slide (0-4). Since the finger chase, nose-finger test, fast alternating hand movements, and heel-shin slide are repeated on both the right and left side, the average of the right and left side assessments are used to derive the total score.

The primary endpoint is the difference between the BHV-4157 and placebo groups in the change from baseline to Week 8 in the total SARA score. The principal analysis will be carried out via a Mixed Model for Repeated Measures (MMRM).

4.6.2. Secondary Efficacy Endpoint

4.6.2.1. Patient Global Impression of Change (PGI-C)

The patient's impression of benefit via the PGI-C will be summarized descriptively by postbaseline visit for the Randomization and Extension Phases, separately, including the number and percentage of subjects in each category:

- No change (or condition has gotten worse)
- Almost the same, hardly any change at all
- A little better, but no noticeable change
- Somewhat better, but the change has not made any real difference
- Moderately better, and a slight but noticeable change
- Better and a definitive improvement that has made a real and worthwhile difference
- A great deal better and a considerable improvement that has made all the difference at each post-baseline study visit

The significance of the difference between treatment groups in the PGI-C scores will be assessed via an exact Wilcoxon rank-sum test and p-values reported for the Randomization Phase only.

4.8. Safety and Other Analyses

Safety and other exploratory analyses will be conducted on the Safety Population. All safety and other data will be listed for the Randomization and Extension phase, separately.

Safety outcome measures include: extent of exposure, compliance to study treatment, adverse events, laboratory assessments, physical examinations, vital signs, ECGs, concomitant medications, and the S-STS questionnaire.

Baseline is considered as the last visit prior to dosing, either the Visit 1 or Visit 2 assessment, for the Randomization Phase. For the Extension Phase, baseline is considered as the visit prior to Extension Visit 1:

- If less than 14 days elapsed between the Randomization and Extension Phases, then use the Visit 4 (Week 8) assessment during the Randomization Phase, or
- If 14 or more days elapsed between the Randomization and Extension Phases, then use the Repeat Baseline assessment at the beginning of the Extension Phase.

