4.8.1. Extent of Exposure and Compliance to Study Treatment

Subjects will receive placebo (QD) or BHV-4157 (140 mg QD) during the Randomization phase. Subjects who complete 8 weeks of treatment in the Randomization phase may be eligible for an open-label Extension phase of the study.

For the Randomization phase, the extent of subject exposure to study treatment will be quantified as the number of days on study drug (placebo or BHV-4157) and measured from the time the subject received the first dose until the time the subject received the last dose, either at the end of 8 weeks of treatment or withdrawal from the Randomization phase.

For the Extension phase, the extent of subject exposure to study treatment will be quantified as the number of days on study drug (BHV-4157) and measured from the time the subject received the first dose of BHV-4157 until the time the subject received the last dose, either at the end of the study or withdrawal from the Extension phase.

The number of tablets taken will be summarized for both the Randomization and Extension phases, separately. Additionally, percent (%) compliance will be calculated and summarized as follows:

Randomization phase % compliance = number of tablets taken during the Randomization phase / (last dose date – first dose date + 1) \times 100.

Extension phase % compliance = number of tablets taken during the Extension phase / (last dose date – first dose date + 1) \times 100.

Overall % compliance = number of tablets taken during the study / [(last dose date – first dose date + 1) – (number of days with a dosing break in dosing between the Randomization and Extension phases)].

Study drug administration and compliance will be listed in subject data listings for the Randomization and Extension Phases, separately.

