4.8.2. Adverse Events

Adverse eventss will be coded using MedDRA and displayed in tables and listings by system organ class (SOC) and preferred term (PT).

Analyses of AEs will be performed for those events that are considered treatment-emergent, where treatment-emergent is defined as any AE that developed, worsened, or became serious after first dose of test treatment.

Adverse events are summarized by subject incidence rates; therefore, in any tabulation, a subject contributes only once to the count for a given AE (SOC or PT).

The number and percentage of subjects with the following on-treatment AEs will be summarized by treatment group and overall for the Randomization and Extension Phases, separately.

- Treatment-emergent AEs,
- AEs related to treatment (definitely, probably, or possibly),
- SAEs,
- AEs with Grade 2 or greater severity,
- AEs leading to discontinuation, and
- Standardized MedDRA query (SMQ) of interstitial lung disease, including eosinophilic pneumonia

On-treatment AEs are AEs with a start date prior to 30 days after the last dose of study drug. For the Randomization Phase, treatment-emergent AEs will be assessed from the date of randomization until: 1) the first day of the Extension Phase or 2) if the subject did not continue into the Extension Phase, 30 days after the last dose of study drug. For the Extension Phase, treatment-emergent AEs will be assessed from the first day of the Extension Phase until 30 days after the last dose of study drug.

In the above tabulations, each subject will contribute only once (i.e., the most related occurrence or the most severe occurrence) to each of the incidence rates in the descriptive analysis, regardless of the number of episodes. No formal hypothesis-testing analysis of AEs incidence rates will be performed.

All AEs occurring pre-treatment, during the Randomization phase, during the Extension phase, and throughout the entire study will be listed. Additional listings will be provided for the Randomization and Extension Phases, including deaths, SAEs, and AEs leading to withdrawal of study drug.

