4.8.3. Laboratory Data

Clinical laboratory evaluations include:

- Hematology: hemoglobin, hematocrit, platelets, complete blood count with differential and absolute neutrophil count
- Serum Chemistry: sodium, potassium, chloride, calcium, alanine aminotransferase (ALT), aspartate aminotransferase (AST), lactate dehydrogenase (LDH), alkaline phosphatase (ALP), gamma-glutamyl transferase (GGT), phosphorous, bicarbonate, creatine phosphokinase (CPK), total protein, albumin, total bilirubin (if greater than 2 mg/dl bilirubin will be fractionated), glucose, creatinine, blood urine nitrogen (BUN), uric acid, and pregnancy testing (for women of child-bearing potential). Additionally at screening, total cholesterol, low-density lipoprotein (LDL), high-density lipoprotein (HDL), triglycerides, folate, hemoglobin A1c (HbA1C), P-Amylase, Lipase, thyroid-stimulation hormone (TSH), and T4
- Urinalysis: pH, specific gravity, protein, ketones, glucose, blood, and microscopic exam (completed only if any part of the urinalysis is not negative)
- Additional tests: human immunodeficiency virus (HIV), hepatitis B surface antigen (HBsAg), and hepatitis C virus (HCV) antibody at screening

Clinical laboratory values will be expressed using conventional units. In the event of repeat values within the same analysis visit, the measurement closest to the target day for the analysis visit interval will be used.

On-treatment laboratory abnormalities are those with an assessment date after the date/time of first dose of study drug and within 30 days after the last dose of study drug. For the Randomization Phase, treatment-emergent laboratory abnormalities will be assessed from the date of randomization until: 1) the first day of the Extension Phase or 2) if the subject did not continue into the Extension Phase, 30 days after the last dose of study drug. For the Extension Phase, treatment-emergent lab abnormalities will be assessed from the first day of the Extension Phase, treatment-emergent lab abnormalities will be assessed from the first day of the Extension Phase until 30 days after the last dose of study drug.

The observed value and change from baseline will be summarized for each continuous laboratory parameter for the Randomization and Extension Phases, separately. In addition, the shift from baseline for laboratory abnormalities (low, normal, high) will be tabulated for the Randomization and Extension Phases, separately.

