For the liver function tests, AST and ALT, the shift from baseline will be presented by visit and to the maximum observed abnormality for the Randomization and Extension Phases, separately. Additionally for ALT, the shift from baseline to the maximum observed treatment-emergent abnormality, regardless of phase, will be presented for subjects treated with BHV4157 only. The following categories will be used to summarize the shift from baseline based on the upper limit of normal (ULN) range:

- Normal
- >ULN to \leq 3x ULN
- >3x ULN to $\le 5x$ ULN
- >5x ULN

All laboratory data will be presented in data listings. Additional listings will be presented for all abnormal laboratory values for the Randomization and Extension Phases, separately. Subjects with a maximum value of ALT or AST >3x ULN and a maximum total bilirubin value >2x

ULN observed at any point during the entire study will also be presented in a listing. Note that these abnormalities do not need to occur on concurrent visits.

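### Does the cross-phase ALT shift table need a stated baseline, and does the Week 8 Extension baseline distort the laboratory shift tables?

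*SAP*

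**What the plan says.** **Baselines.** SAP 4.8 uses the Visit 1 or Visit 2 value before dosing for the Randomization Phase. For the Extension it says "If less than 14 days elapsed between the Randomization and Extension Phases, then use the Visit 4 (Week 8) assessment during the Randomization Phase"; with a longer gap, the Repeat Baseline applies. SAP 2.1 requires no wash-out before the Extension, so the short-gap rule is the usual route.

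**Shift tables.** SAP 4.8.3 states that "the shift from baseline for laboratory abnormalities (low, normal, high) will be tabulated for the Randomization and Extension Phases, separately". On transaminases it says: "For the liver function tests, AST and ALT, the shift from baseline will be presented by visit and to the maximum observed abnormality", again for each phase. For ALT alone it adds a shift from baseline to "the maximum observed treatment-emergent abnormality, regardless of phase, will be presented for subjects treated with BHV4157 only".

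**Windows.** SAP 4.8.3 says "On-treatment laboratory abnormalities are those with an assessment date after the date/time of first dose of study drug" and up to 30 days after the last dose. For the Randomization Phase, "treatment-emergent laboratory abnormalities will be assessed from the date of randomization until" the first Extension day, or 30 days after the last dose for subjects who do not continue. SAP 4.8.1 uses the term study drug to cover placebo as well.

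**Grouping.** SAP 4.8.2 says that AE counts "will be summarized by treatment group and overall for the Randomization and Extension Phases, separately". The visible laboratory text names no grouping. Protocol 9.1 plans combined-phase summaries for patients who receive troriluzole in both phases.

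**The concern.** Three things look wrong at first.

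- The cross-phase ALT table needs one baseline per subject, but SAP 4.8 defines baselines only by phase. Two programmers could put the same subject in different cells.
- The window opens at randomization and study drug includes placebo. A peak during the placebo weeks of a subject who later took troriluzole could therefore be shown as a troriluzole maximum. Conversely, a Week 8 baseline could absorb a rise during the first 8 weeks on drug.
- AST has the same per-phase tables as ALT but no cross-phase table. In the Extension tables, a Week 8 baseline means different things in the two randomised arms.

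Protocol 6.2.4.5 singles out transaminase elevation as a known effect of riluzole, with rates of about 8% above 3x ULN and 2% above 5x ULN. A table meant to show the worst ALT on drug should not rest on a guess.

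**Working it through.** The plan states no figure here, so there is none to reproduce. The check sets the definitions side by side and then sizes the open point.

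**1. Who is in the cross-phase table.** Its closing words allow two readings.
- (a) Subjects who received only BHV4157, that is, in both phases. This is the group in Protocol 9.1. No placebo period exists, and the only pre-drug baseline is Visit 1/2.
- (b) Subjects who ever received BHV4157. Placebo-first subjects then enter.

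**2. Which baseline.** The natural choice for a table about BHV4157 is the last value before the first BHV4157 dose. SAP 4.8 already supplies it:
- randomised to BHV4157: the Randomization baseline, Visit 1/2;
- randomised to placebo: the Extension baseline, which is Week 8, or the Repeat Baseline if 14 or more days elapsed.

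**3. How much placebo-period data could enter under (b).** Scheduled post-randomization ALT draws (Protocol Tables 2 and 3, Section 6.2.4.5):
- Randomization Weeks 4 and 8 = 2
- Extension Weeks 4, 8, 12, 24, 36 and 48 = 6
- Share on placebo for a placebo-first subject = 2/(2 + 6) = 25%

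A continuing subject followed to Week 192 has 12 more draws (Protocol Table 4, every 12 weeks from Week 60), so the share is 2/20 = 10%. These are shares of draws, not of subjects or of peaks.

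**4. What it could do to a cell.** The values below are invented; the categories are from SAP 4.8.3.
- *Example A*, placebo-first: Visit 2 0.8x ULN, Week 4 3.2x, Week 8 0.9x, Extension maximum 1.5x. Either baseline is Normal. With placebo weeks, the maximum is 3.2x and the shift is two categories. Without them, the maximum is 1.5x and the shift is one category.
- *Example B*, troriluzole-first: Visit 2 0.8x, Week 8 2.9x, Extension maximum 3.1x. The shift is two categories from Visit 2 and one from Week 8. The Week 8 choice would place the baseline inside the period being summarised. SAP 4.8 ties Week 8 to the Extension Phase, so nothing directs that choice.

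**5. Rough size under (b).** Assume 60 placebo-first subjects (120 randomised 1:1, all entering the Extension) and an independent chance q per draw of ALT above ULN. The documents give no such rate. The expected number whose only elevation through Extension Week 48 falls in the placebo weeks is 60 × [1 − (1 − q)²] × (1 − q)⁶.

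| q (assumed) | Expected subjects |
|---|---|
| 1% | 1.1 |
| 2% | 2.1 |
| 5% | 4.3 |
| 10% | 6.1 |

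These count any value above ULN, and the same values also appear in the Randomization Phase tables.

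**6. AST.** It has by-visit and maximum shifts in each phase. ALT or AST above 3x ULN is an event of special interest (addendum section 12) and triggers a narrative in anyone who took troriluzole (addendum section 8). AST is also in the whole-study listing with bilirubin (SAP 4.8.3). No section promises a cross-phase AST table.

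**7. Extension baseline.** The difference between arms exists only when the gap is under 14 days; at a Repeat Baseline neither arm is being dosed. Within the Extension the tables show change since Extension entry, which is a coherent quantity. Shifts already present by Week 8 are in the Randomization tables. The two meanings mix only if the arms are pooled, and no visible laboratory text says they are. In a phase where everyone takes troriluzole, the AE wording by treatment group most naturally means the randomised arm.

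**The case for a change.** The best case for a change is that the gap in the ALT table is real on the visible text. The ever-treated reading has support: the addendum's BHV4157 cohort and its narrative rule both require only one dose. The addendum's on-treatment definition for safety fixes the end of the window but not its start, so it does not keep placebo weeks out. Under the narrower reading, placebo-first subjects drop out of the only visible cross-phase shift table. One sentence would remove the doubt, and adding AST would need no new data because it is drawn with ALT.

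Part of this stands. The population and baseline are not written down, and Protocol 9.1 makes the narrower reading plausible without proving it. But the randomization-dated window belongs to a sentence about the Randomization Phase. Carrying it unchanged into a cross-phase table is an inference. A cross-phase AST table and display by randomised arm are reasonable extras, but their absence contradicts no rule in the plan.

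**Conclusion.** No change to the plan is needed. The open point is the definition of population and baseline for one descriptive ALT table. An analyst would fill it sensibly with the last value before the first BHV4157 dose and later values only. The Week 8 Extension baseline is an acceptable choice for a phase-specific table, and the lack of a cross-phase AST table loses no marked elevation.

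Under the less favourable reading, up to 2 of 8 scheduled ALT draws per placebo-first subject through Extension Week 48 could enter the table. With assumed background rates of 1% to 10% per draw, that is about 1 to 6 of 60 subjects with an elevation seen only on placebo. No hypothesis test or efficacy conclusion is touched. The number of subjects actually affected cannot be derived from the documents.

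This rests on the visible text. SAP 4.2.3, on pooling, and the content of addendum section 10, on updated analyses, are not shown, and either may already give the definition.

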4.8.1. Extent of Exposure and Compliance to Study Treatment

Subjects will receive placebo (QD) or BHV-4157 (140 mg QD) during the Randomization phase. Subjects who complete 8 weeks of treatment in the Randomization phase may be eligible for an open-label Extension phase of the study.

For the Randomization phase, the extent of subject exposure to study treatment will be quantified as the number of days on study drug (placebo or BHV-4157) and measured from the time the subject received the first dose until the time the subject received the last dose, either at the end of 8 weeks of treatment or withdrawal from the Randomization phase.

For the Extension phase, the extent of subject exposure to study treatment will be quantified as the number of days on study drug (BHV-4157) and measured from the time the subject received the first dose of BHV-4157 until the time the subject received the last dose, either at the end of the study or withdrawal from the Extension phase.

The number of tablets taken will be summarized for both the Randomization and Extension phases, separately. Additionally, percent (%) compliance will be calculated and summarized as follows:

Randomization phase % compliance = number of tablets taken during the Randomization phase / (last dose date – first dose date + 1) \times 100.

Extension phase % compliance = number of tablets taken during the Extension phase / (last dose date – first dose date + 1) \times 100.

Overall % compliance = number of tablets taken during the study / [(last dose date – first dose date + 1) – (number of days with a dosing break in dosing between the Randomization and Extension phases)].

Study drug administration and compliance will be listed in subject data listings for the Randomization and Extension Phases, separately.

4.8.2. Adverse Events

Adverse eventss will be coded using MedDRA and displayed in tables and listings by system organ class (SOC) and preferred term (PT).

Analyses of AEs will be performed for those events that are considered treatment-emergent, where treatment-emergent is defined as any AE that developed, worsened, or became serious after first dose of test treatment.

Adverse events are summarized by subject incidence rates; therefore, in any tabulation, a subject contributes only once to the count for a given AE (SOC or PT).

The number and percentage of subjects with the following on-treatment AEs will be summarized by treatment group and overall for the Randomization and Extension Phases, separately.

- Treatment-emergent AEs,
- AEs related to treatment (definitely, probably, or possibly),
- SAEs,
- AEs with Grade 2 or greater severity,
- AEs leading to discontinuation, and
- Standardized MedDRA query (SMQ) of interstitial lung disease, including eosinophilic pneumonia

On-treatment AEs are AEs with a start date prior to 30 days after the last dose of study drug. For the Randomization Phase, treatment-emergent AEs will be assessed from the date of randomization until: 1) the first day of the Extension Phase or 2) if the subject did not continue into the Extension Phase, 30 days after the last dose of study drug. For the Extension Phase, treatment-emergent AEs will be assessed from the first day of the Extension Phase until 30 days after the last dose of study drug.

In the above tabulations, each subject will contribute only once (i.e., the most related occurrence or the most severe occurrence) to each of the incidence rates in the descriptive analysis, regardless of the number of episodes. No formal hypothesis-testing analysis of AEs incidence rates will be performed.

All AEs occurring pre-treatment, during the Randomization phase, during the Extension phase, and throughout the entire study will be listed. Additional listings will be provided for the Randomization and Extension Phases, including deaths, SAEs, and AEs leading to withdrawal of study drug.

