4 STUDY PLAN

4.1 Study Design and Duration

BHV4157-201 is a Phase IIb/III, multicenter, randomized, double-blind, 2-arm placebo-controlled parallel-group study designed to assess safety, tolerability, and efficacy in a population of patients with Spinocerebellar Ataxia. Subjects will be randomized to receive placebo (QD) or troriluzole (140 mg QD),

Subjects with SCA3 genotype will be limited to comprise up to approximately 10% so that this most common type of SCA is not over-represented.

Dosing will continue for 8 weeks. Subjects will return to the clinic two weeks after discontinuing study medication for a follow-up safety visit. In addition, subjects completing the Randomization Phase will be offered approximately 192 weeks of open-label treatment as long as the PI believes open-label treatment offers an acceptable risk-benefit profile. Subjects who agree to enter the Extension Phase will not complete the follow-up safety visit and should continue dosing as specified.

Subjects entering the Extension Phase would have their first Extension Visit four weeks after the Week 8 Randomization Phase visit. If there is a delay of two weeks or more in dosing between the Randomization Phase and the Extension Phase, subjects would be required to complete an Extension Baseline Visit. Thereafter, subjects will undergo visits every fourth week through Week 12 of this phase. Then subjects will undergo visits every 12 weeks up to Week 192 of this phase. All subjects will undergo a termination visit two weeks after the last dose of study drug.

Subjects who previously completed the extension phase will be allowed to participate in the expanded extension phase for a total of 144 weeks of open-label administration of troriluzole, provided the PI deems this treatment to present an acceptable risk-benefit profile. Such subjects who have been off of medication for at least 2 weeks, will need additional Baseline Visits followed by visits scheduled approximately every 12 weeks, as well as laboratory assessments at approximately 4 and 8 weeks after re-starting medication. In addition, these subjects will be required to have clinical laboratory assessment results that are not deemed clinically significant, available prior to the Baseline Visit and drawn within 6 weeks prior to that visit. These subjects should not have taken riluzole for at least 12 hours prior to re-starting troriluzole.

[figure not shown]

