9.1 General Procedures

Analysis populations: Efficacy data will be assessed using the Full Analysis Set (FAS) consisting of all patients with at least one dose of test treatment and at least one efficacy observation. No missing data will be imputed as missing data are assumed to be missing at random. Safety data will be assessed using the Safety Analysis Set (SAF), which includes all patients exposed to at least 1 dose of study treatment.

Statistical analyses: Descriptive statistics are planned for all outcome measures collected in this study. The randomization phase and the extension phase will be analyzed separately. For patients receiving troriluzole during both phases, summary statistics will be provided for data from both phases combined.

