9.3.3 Analysis of Safety

Safety outcome measures (adverse events, laboratory variables, ECG and vital signs) will be descriptively summarized by treatment group for the SAF population. For adverse events, treatment-emergent adverse events (TEAEs) are defined as those that developed, worsened, or became serious after first dose of test treatment. They will be summarized by counts and percents. Observed values and change from baseline in lab variables and vital signs will be summarized by count, mean, median, SD, minimum, and maximum. The primary endpoint will be assessed when all subjects complete the 8 week randomization phase. In addition, during the extension phase, data may be locked, analyses conducted, and reports produced as required to support safety monitoring, administrative concerns, and regulatory requirements.

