2. STUDY DESIGN

2.1. Synopsis of Study Design

BHV4157-201 is a Phase IIb/III, multicenter, randomized, double-blind, 2-arm placebocontrolled parallel-group study designed to assess safety, tolerability, and efficacy signals in a population of subjects with SCA.

Subjects who are determined to be eligible for the study will enter the Randomization Phase. Dosing will continue for 8 weeks. Subjects will return to the clinic 2 weeks after discontinuing study medication for a follow-up safety visit (see Figure 1). In addition, subjects completing the Randomization Phase will be offered 48 weeks of open-label treatment given the principle investigator believes open-label treatment offers an acceptable risk-benefit profile. Subjects who agree to enter the Extension Phase will not be required to wash-out of drug or complete the follow-up safety visit, but instead should continue dosing as specified in the Extension Phase.

Subjects entering the Extension Phase will have their first Extension visit 4 weeks after the Week 8 Randomization Phase visit. If there is a delay of two weeks or more in dosing between the Randomization Phase and the Extension Phase, then subjects will be required to complete an Extension baseline visit. Thereafter, subjects will undergo visits every fourth week through Week 12 of this phase. Then subjects will undergo visits every 12 weeks up to Week 48 of this phase. All subjects will undergo a post study drug termination visit two weeks after the last dose of study drug in the Extension Phase.

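### Extension adverse events are planned only as crude percentages of subjects over follow-up that can reach 192 weeks, and the readable AE section has no combined-phase troriluzole table

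*SAP*

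**What the plan says.** **Measure.** SAP 4.8.2 states that "Adverse events are summarized by subject incidence rates; therefore, in any tabulation, a subject contributes only once to the count for a given AE". On-treatment events "will be summarized by treatment group and overall for the Randomization and Extension Phases, separately". What the SAP calls an incidence rate is thus a percentage of subjects, with no person-time in the denominator. Protocol 9.3.3 says the same of treatment-emergent events: "They will be summarized by counts and percents".

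**Window.** For the Extension, "treatment-emergent AEs will be assessed from the first day of the Extension Phase until 30 days after the last dose of study drug". SAP 4.3 places the Extension summary after the last subject's final visit or discontinuation. Events "during the Extension phase, and throughout the entire study will be listed", so the only whole-study AE output in that section is a listing.

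**Length of follow-up.** SAP 2.1 says that "subjects completing the Randomization Phase will be offered 48 weeks of open-label treatment". In protocol 4.1 subjects are "offered approximately 192 weeks of open-label treatment", and protocol 4.4 gives 144 weeks for returning subjects.

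**Combined phases.** Protocol 9.1: "For patients receiving troriluzole during both phases, summary statistics will be provided for data from both phases combined". In the readable SAP, two summary outputs cross the phases: an ALT shift table for subjects treated with the drug (4.8.3) and an overall compliance figure (4.8.1). Section 4.8.1 also quantifies days on drug in each phase but does not link them to AE counts. The addendum's readable adverse-event section changes only the definition of a treatment-related event.

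**The concern.** A percentage of subjects with an event is easy to read when everyone is followed for about the same time. In the Extension they are not: some subjects leave early, some stop at 48 weeks, some return after a gap, and some may continue to 192 weeks. The percentage then depends on how long people stayed as well as on how often events occur. Protocol 9.3.3 also allows data cuts during the Extension, and percentages from different cuts would differ for the same reason.

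The phase split adds two difficulties for anyone who wants a troriluzole AE profile:

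- The Extension table leaves out the first 8 weeks on drug for subjects randomised to troriluzole but includes the first 8 weeks for subjects randomised to placebo.
- The two phase tables cannot be added, because a subject with the same event in both phases counts in each.

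Frequency and severity of adverse events is a named secondary endpoint (protocol 3.2, SAP 2.4.1). Long-term open-label exposure is most of the troriluzole experience that this trial will produce.

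**Working it through.** The documents give no AE rate and no expected Extension exposure, so there is no plan figure to reproduce here. The rates and dropout below are assumptions, shown as ranges.

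**1. Inputs from the documents.** Randomization Phase 8 weeks (protocol 4.1); Extension 48 weeks in SAP 2.1, and up to 192 weeks, or 144 for returning subjects, in protocol 4.4. The longest Extension window is 192/8 = 24 times the randomised phase and 192/48 = 4 times the length that SAP v2.0 assumed.

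**2. Crude percentage at a constant rate, full follow-up.** With rate r per patient-year and t = weeks × 7/365.25, crude % = 100 × [1 − exp(−r t)]. At 192 weeks t = 3.68 years, so r = 0.10 gives 1 − exp(−0.368) = 30.8%.

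| Assumed rate per 100 patient-years | 8 wk | 48 wk | 144 wk | 192 wk |
|---|---|---|---|---|
| 5 | 0.8% | 4.5% | 12.9% | 16.8% |
| 10 | 1.5% | 8.8% | 24.1% | 30.8% |
| 20 | 3.0% | 16.8% | 42.4% | 52.1% |
| 50 | 7.4% | 36.9% | 74.8% | 84.1% |

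Risk is constant along each row; only follow-up changes.

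**3. The reverse.** A crude 20% implies a rate of −ln(0.80)/t: 145.5 per 100 patient-years over 8 weeks, 24.3 over 48, 8.1 over 144 and 6.1 over 192. Without exposure, the percentage does not identify a rate.

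**4. Early exit.** Let a fraction d leave per 48 weeks, so the exit rate is h = −ln(1 − d)/(48 × 7/365.25). Then crude % = 100 × r/(r + h) × [1 − exp(−(r + h)t)]. At r = 0.10 and 192 weeks:

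| Assumed dropout per 48 weeks | Crude % | Patient-years at risk per subject | Rate per 100 patient-years |
|---|---|---|---|
| 10% | 25.4% | 2.54 | 10 |
| 20% | 20.9% | 2.09 | 10 |
| 30% | 17.1% | 1.71 | 10 |
| 40% | 13.9% | 1.39 | 10 |

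Retention alone moves the crude figure by 11.5 percentage points. The rate does not move.

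**5. Returning subjects.** Read literally, the SAP's Extension AE window runs unbroken from the first Extension day to 30 days after the last dose, and so takes in the off-drug gap before re-entry. Extension exposure in SAP 4.8.1, measured from first to last dose, does the same. The overall compliance formula subtracts only the break between Randomization and Extension. Addendum section 4 does account for the break before the Expanded Extension in its FAS cohort, but the readable text makes no matching change for AEs.

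**The case against.** Four replies have weight.

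**The randomised comparison is sound.** A reader might infer that the plan yields no interpretable troriluzole AE figure at all. The documents do not support that. Both arms have the same planned 8 weeks, and SAP 4.2.8 expects data loss below 10% in that phase, so crude percentages compare the arms fairly. This stands in full.

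**The combined summary may be in text that cannot be read.** A reader might infer that the SAP dropped the protocol 9.1 commitment. That cannot be shown. The SAP contents list a section 4.2.3 on pooling data, whose text is not in the public copy, and addendum section 10 announces updates that are not readable. All that can be said is that the readable AE section shows no such table.

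**Crude percentages are the protocol's choice.** A reader might see a conflict between SAP and protocol. There is none on the measure, because protocol 9.3.3 asks for counts and percentages. Person-time rates would be an addition.

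**The size is easily overstated.** Setting 30.8% against 1.5% suggests a spread of about 20-fold. That needs one assumed rate, full follow-up for everyone, and a comparison across phases that neither document plans. With the dropout range above it falls to about 17-fold (25.4/1.5) to 9-fold (13.9/1.5); at 50 per 100 patient-years with full follow-up it is about 11-fold (84.1/7.4). If treatment group in the Extension means randomised group, the uneven handling of the first 8 drug weeks falls mainly on the overall column.

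Version timing explains only part. The 192 weeks came with protocol version 08 (17 April 2020), after the addendum (27 March 2020). But version 08 added 48 weeks, so version 7.0, which the addendum cites, already ran to 192 − 48 = 144 weeks for continuing subjects, three times the 48 in SAP v2.0.

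Finally, per-phase exposure and full listings would let someone derive a rate later. None is pre-specified, and total days on drug are not time at risk to first event.

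**Conclusion.** The point holds for the Extension and for any all-troriluzole AE summary, and not for the 8-week randomised comparison. As planned, Extension percentages mix risk with follow-up that varies between subjects and may reach four times the length assumed in SAP v2.0. At an assumed 10 per 100 patient-years with full follow-up, moving from 48 to 192 weeks raises the crude figure about 3.5-fold (30.8/8.8). These sizes rest on assumed constant rates and assumed dropout; the direction does not depend on the values chosen. Whether the summary promised in protocol 9.1 is specified for AEs is open, because the sections where it might stand are not readable. This is a worthwhile, inexpensive improvement to safety reporting, with no bearing on the primary analysis.

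**What to change.** Update SAP 4.8.2 to the current Extension length and the re-entry pathway, and add one table:

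- Treatment-emergent AEs counted from the first troriluzole dose, whether randomised or open-label.
- Subjects with the event per 100 patient-years at risk, censored at first event. Exclude off-drug gaps before re-entry, and count events and person-time over the same window.
- Columns by randomised group and overall. The troriluzole-randomised column then supplies the both-phases summary of protocol 9.1. If SAP 4.2.3 or addendum section 10 already specifies that summary, cross-refer to it.
- Time on 280 mg shown separately, since the protocol allows that dose for some Extension subjects.
- Crude percentages kept beside the rates, and the 8-week placebo rate shown for context only.

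The cost is one more table per AE category, from data already collected. The drawback is that a person-time rate assumes a roughly constant hazard: events concentrated soon after starting the drug would be diluted by long follow-up. That is a reason to keep the crude column and not to treat the placebo rate as a formal comparator.
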